## 1.6 CLINICAL PHARMACOLOGY

Please see the ZX008 IB for details on clinical pharmacology. Below are the clinical pharmacology conclusions.

- Coadministration of ZX008 with the STP regimen (STP with CLB and/or VPA) resulted in an increased fenfluramine and decreased norfenfluramine concentrations, and therefore a dose adjustment is used in the clinical trials.
- STP is the predominant perpetrator of the interaction; while VPA and CLB do not have a significant independent impact on the PK of fenfluramine or norfenfluramine, whether administered with or without STP.
- Coadministration of ZX008 with CBD at steady state resulted in increased fenfluramine concentrations but this increase was within the range of [REDACTED] dosing used in Study 1504 Cohort 2; thus, no dose adjustment is recommended when fenfluramine is coadministered with CBD.

- In the population PK analysis, intrinsic patient factors (age, gender, race/ethnicity, and BMI) demonstrated no substantial impact on the clearance or exposure to fenfluramine or norfenfluramine when dosed on a mg/kg basis to a maximum of 30 mg/day.
- ZX008 had no effect on QTc intervals at either the therapeutic or supratherapeutic dose, and no relationship was observed between fenfluramine or norfenfluramine exposure and QTcF.
- ZX008 exhibited approximately dose proportional PK over a 4-fold range of doses (15 to 120 mg/day).
- CYP450 metabolizer genotype for CYP1A2, CYP2B6, CYP2C19, CYP2D6, or CYP3A4 had no impact on the PK of fenfluramine or norfenfluramine.

### **1.7 BACKGROUND INFORMATION ON REFERENCE PRODUCT**

Not applicable.

### **1.8 RATIONALE FOR CURRENT STUDY**

The rationale for conducting this open-label extension study is primarily to evaluate the long-term safety of ZX008 in DS. This protocol also provides the opportunity for continued treatment for subjects responding to treatment from the Phase 3 double-blind studies, and an opportunity for initial treatment with ZX008 for subjects randomized to placebo in those studies.

### **1.9 RATIONALE FOR INCLUDING DE NOVO SUBJECTS**

Subjects who are >18 to ≤35 years of age at the time of screening, and who meet all other eligibility criteria may be eligible for participation after discussion with the Medical Monitor and sponsor about the potential risks and benefits for receiving ZX008. Participation for these subjects will be at the discretion of the sponsor.

Epileptic seizures tend to become less frequent and less severe after childhood; however, the mortality rate remains high. One study on the long-term outcome of 24 adult patients with DS reported 5 (20.8%) deaths, at a mean age of 24.8 years, one by status epilepticus, three by sudden unexpected death in epilepsy (SUDEP), and one of unknown cause ([Genton 2011](#)).

Fever sensitivity (temperature variations) persists throughout the clinical course of DS, but its impact on seizure frequency and severity is milder than in infancy. Generalized convulsive seizures, mostly reported as generalized tonic-clonic seizures persist, often with a focal onset but are less frequent than in childhood and mostly nocturnal. Some of these major convulsive seizures have less typical aspects, for example, bilateral or asymmetric tonic posturing, followed in some cases by a tonic vibratory state or clonic movements ([Oguni 2001](#);

Akiyama 2010). Other seizures like myoclonic seizures, atypical absences, and complex partial seizures are less common in adulthood. Motor abnormalities are also common in adulthood, as is intellectual disability. Dependency in adulthood is nearly constant.

Including subjects >18 to ≤35 years of age provides the opportunity to investigate the impact of ZX008 on DS outcomes as subjects transition to adulthood.

## 1.10 RISK-BENEFIT ASSESSMENT

Fenfluramine has been used successfully for up to 30 years in Belgium in refractory pediatric epilepsy patients, including those with DS (Boel 1996, Ceulemans 2012, Ceulemans 2016, Schoonjans 2016, Schoonjans 2017). The efficacy and safety of this therapeutic approach has been reported to be overwhelmingly favorable. Of the 15 DS treated patients, 10 (67%) were reported as seizure-free, with the average time of seizure-freedom being 6 years (range 1-19 years). Twelve patients (87%) had a greater than 90% reduction in seizure frequency and 14 patients (93%) with greater than 70% reduction in seizure frequency. No patients experienced emergence of clinical valvulopathy or pulmonary hypertension. The doses tested thus far in DS range from 0.12 to 0.9 mg/kg/day in subjects over 1 year of age to adults. Fenfluramine has also been administered to over 500 children with neurobehavioral conditions, including autism and ADHD with good safety and tolerability. Doses tested in these pediatric studies ranged from 0.65 mg/kg/day to 3.6 mg/kg/day, but a commonly used dose was 1.5 mg/kg/day. Occasionally, fixed doses of 30 to 80 mg were used.

In addition, ZX008 demonstrated a statistically significant and clinically meaningful reduction in monthly convulsive seizure frequency in Study 1 and Study 1504 Cohort 2 and was generally well tolerated. There was no clinical or echocardiographic evidence of cardiac valvulopathy or pulmonary hypertension and no patient discontinued participation or required a change in monitoring in the study due to cardiac factors. The PK exposure associated with the doses of ZX008 in the DS studies of 0.2 mg/kg/day to 0.8 mg/kg/day administered orally [in equally divided doses twice per day (BID)] is expected to be lower than that obtained at the doses used in the past for the treatment of obesity in adults and of neurobehavioral conditions in children and adolescents (ZX008 IB). The doses used in this study are based on the data from the DS patients being successfully treated in Belgium discussed above and supported by results from Study 1 and Study 1504 Cohort 2.

Interim results from this open-label study show that the effects observed during the double-blind studies were durable and long-lasting; the reduction in convulsive seizures for subjects in Study 1503 was maintained throughout study participation of up to 3 years at the time of the interim analysis, with no evidence for developing tolerance. The pharmacologic and toxicological profile for the active pharmaceutical ingredient, fenfluramine, following oral administration is well established (ZX008 IB).

The safety monitoring practices employed by this protocol are adequate to protect the subjects' safety and should detect expected and unexpected treatment-emergent adverse events. Subjects will be enrolled into this study from the core studies where they had been transitioned to the lowest dose of ZX008 (0.2 mg/kg/day; maximum 30 mg/day or 20 mg/day for subjects from ZX008-1504 Cohort 1 dose regimen 3 or Cohort 2) and will remain on this dose for the first month of this study. After this time, the dose of ZX008 may be adjusted based on effectiveness and tolerability. For subjects that participated in core studies ZX008-1501, ZX008-1502, and dose regimen 1 or 2 from Cohort 1 of ZX008-1504 dose increases may be made in increments of 0.2 mg/kg/day, to a maximum of 0.8 mg/kg/day (maximum dose 30 mg/day), and these increases should not occur earlier than every 14 days at each dose level. For subjects that participated in core study ZX008-1504 Cohort 1 dose regimen 3 and Cohort 2 and are receiving concomitant STP the first dose change will be to 0.4 mg/kg/day and the final dose change will be to 0.5 mg/kg/day, but not to exceed 20 mg/day. Dose increases may only occur after a review of the diary and reported adverse events (AEs), and if, in the investigator's opinion, seizure frequency, severity, and/or duration indicates a change in medication regimen is warranted. Dose decreases for tolerability can occur at the investigator's discretion, in dose amounts and frequency appropriate for the situation. Dose adjustments outside of these parameters must be discussed with the Medical Monitor prior to initiation.

It is acknowledged that the initial dose of ZX008 in this study, 0.2 mg/kg/day, may or may not be effective or may be less effective than 0.8 mg/kg/day (or 0.5 mg/kg/day for subjects taking concomitant STP) for some subjects and some subjects may experience a worsening of their seizure condition after transitioning to the lower dose. However, there is benefit in identifying a minimally effective dose for all subjects in the study since the cardiotoxicity of fenfluramine appears to be dose-related in adults. The dosing instructions of this protocol permit dose adjustment during the first month of fixed dosing at 0.2 mg/kg/day if a clinically meaningful worsening occurs, such as an increase in frequency, severity or duration of existing seizures, or emergence of a new seizure type.

The approximate volume of blood (240 mL) planned for collection from each subject over the course of the entire study (approximately 3 years, but not including repeat or additional tests ordered by the investigator) presents no undue risk to the subjects.

The ZX008 0.2 mg/kg/day, 0.4 mg/kg/day, 0.6 mg/kg/day, 0.8 mg/kg/day, and 0.5 mg/kg/day (in subjects taking concomitant STP) doses are believed to be therapeutic doses, which could provide sufficient anti-epileptic support for a sustained period of time during the study.

The available information suggests that the present clinical study has an acceptable risk-benefit ratio.

## 2. STUDY OBJECTIVES AND ENDPOINTS

### 2.1 PRIMARY OBJECTIVE

The primary objective of the study is:

- To assess the long-term safety and tolerability of ZX008.

### 2.2 SECONDARY OBJECTIVES

The secondary objectives of the study are:

- To assess the effect of ZX008 relative to the pre-ZX008 baseline on the following effectiveness measures:
  - The change in the frequency of convulsive seizures from Visit 3 to Visit 8 (ie, Day 31 to Day 365) and for the entire Year 1 treatment period (ie, Visit 1/Day 1 to Visit 8/Day 365)
  - The proportion of subjects who achieve a  $\geq 40\%$ ,  $\geq 50\%$ , and  $\geq 75\%$  reduction in convulsive seizure frequency
  - The longest convulsive seizure-free interval
  - The percentage of convulsive seizure-free days
  - The non-convulsive seizure frequency
  - The convulsive + non-convulsive seizure frequency
- To estimate the incidence of the following on subjects receiving ZX008:
  - Use of rescue medication
  - Hospitalization to treat seizures
  - Status epilepticus (SE)
- To assess the effect of ZX008 relative to the pre-ZX008 baseline on the following QoL measures:
  - Quality of Life in Childhood Epilepsy (QOLCE) score
  - Pediatric Quality of Life Inventory™ (PedsQL score)
  - PedsQL Family Impact module score
  - QoL of the parent/caregiver using the standardized measure of health status (EQ-5D-5L scale)
  - Affective symptoms of the parent/caregiver using the Hospital Anxiety and Depression Scale (HADS)
- To assess the effect of ZX008 on the following QoL measures:
  - Clinical Global Impression – Improvement (CGI-I) rating, as assessed by the principal investigator
  - CGI-I rating, as assessed by the parent/caregiver

## 2.3 EXPLORATORY OBJECTIVES

The exploratory objectives for subjects who participated in core study ZX008-1504 are:

- To assess the effect of ZX008 on the following QoL measures:
  - Sleep quality and mealtime behavior, as assessed by the parent/caregiver
  - Karolinska Sleep Scale
  - Health and social care resource use (These measures include planned and unplanned hospital visits, use of ambulances, General Practitioner (GP) visits, speech and language therapy utilization, occupational and physical therapy utilization)

## 2.4 STUDY ENDPOINTS

### 2.4.1 Effectiveness Endpoints

The effectiveness endpoints of the study are:

- Number of seizures by type
- Convulsive seizure-free interval
- CGI-I as assessed by parent/caregiver
- CGI-I as assessed by principal investigator
- QOLCE to measure changes in quality of life of the subject
- PedsQL to measure changes in quality of life of the subject
- PedsQL Family Impact module to measure changes in quality of life of the parent/caregiver
- QoL of parent/caregiver using the EQ-5D-5L scale
- Affective symptoms of parent/caregiver using the HADS (in parents/caregivers from core studies ZX008-1501 and ZX008-1502 only)
- Duration of prolonged seizures (seizure type that, during pre-Z008 baseline, had duration > 2 minutes)
- Number of episodes of SE
- Number of instances of rescue medication use and number of doses
- Number of inpatient hospital admissions due to seizures

### 2.4.2 Safety Endpoints

The safety endpoints of the study are:

- AEs
- Laboratory safety (hematology, chemistry, urinalysis)
- Vital signs (blood pressure, heart rate, temperature, and respiratory rate)
- Physical examination
- Neurological examination

- 12-lead electrocardiogram (ECGs)
- Doppler echocardiogram (ECHOs)
- Body weight
- Behavior Rating Inventory for Executive Function (BRIEF) to measure cognition

### **2.4.3 Exploratory Endpoints**

For subjects who participated in core study ZX008-1504 only, the exploratory endpoints of this study are:

- Health and social care resource use, including GP visits, speech and language, occupational and physical therapy, in addition to acute hospital and institutional length of stay, loss of work, etc.
- Sleep quality
- Mealtime behavior
- Karolinska Sleepiness Scale to measure the effect of study medication on sleepiness

### 3. INVESTIGATIONAL PLAN

#### 3.1 OVERALL STUDY DESIGN AND PLAN

This is an international, multicenter, open-label, long-term safety study of ZX008 in pediatric and young adult subjects with DS. Subjects eligible for participation are those who have successfully completed 14 weeks of treatment in core studies ZX008-1501 or ZX008-1502, and 15 weeks of treatment in core study ZX008-1504 Cohort 2, or successfully completed core study ZX008-1504 Cohort 1, and are candidates for continuous treatment for an extended period of time. In addition, subjects who are >18 to ≤35 years of age at the time of screening, and who meet all other eligibility criteria may be eligible for participation after discussion with the Medical Monitor and sponsor about the potential risks and benefits for receiving ZX008. Participation for these subjects will be at the discretion of the sponsor.

This trial will consist of an up to 36-month open-label extension (OLE) Treatment Period and a 2-week Post-Dosing Period. Thus, subjects who complete this trial will have been treated with ZX008 for a minimum of up to 3 years (including their participation in both the core study and this study). Subjects who did not participate in one of the core studies will undergo a screening period up to 28 days to confirm eligibility prior to receiving their first dose in the OLE Treatment Period

During the OLE Treatment Period, all subjects will be treated initially with 0.2 mg/kg/day for 1 month to assess effectiveness of this dose in all study subjects. After 1 month at a dose of 0.2 mg/kg/day, the investigator may adjust the dose of each subject based on effectiveness and tolerability. For subjects who are not receiving concomitant STP, including de novo subjects and those who participated in core studies ZX008-1501, ZX008-1502, and dose regimen 1 or 2 from Cohort 1 of ZX008-1504, dose changes should be made in increments of 0.2 mg/kg/day, to a maximum of 0.8 mg/kg/day but not to exceed total dose of 30 mg/day. For subjects who are receiving concomitant STP, including de novo subjects and those who participated in core study ZX008-1504 Cohort 1 dose regimen 3 and Cohort 2, and the first dose change will be to 0.4 mg/kg/day and the final dose change will be to 0.5 mg/kg/day, but not to exceed 20 mg/day. Dose increases should not occur earlier than every 14 days at each dose level. Dose increases may only occur after a review of the diary and reported AEs, and if, in the investigator's opinion, seizure frequency, severity, and/or duration indicates a change in medication regimen is warranted. Dose decreases for tolerability can occur at the investigator's discretion, in dose amounts and frequency appropriate for the situation. ZX008 dose adjustments outside of these parameters should be discussed with the Medical Monitor prior to initiation.

In addition, if a subject has been stable on the same dose of ZX008 for 6 months or longer, investigators may adjust the doses of one or more of the other concomitant AEDs as per typical clinical practice. Concomitant AEDs may be withdrawn completely but all subjects must remain on a minimum of 1 concomitant AED plus ZX008. No new concomitant AEDs or

antiepileptic treatments may be introduced while in this study. All medication dose changes must be documented with a clinical explanation and justification. Concomitant AED dose adjustments outside of these parameters should be discussed with the Medical Monitor prior to initiation.

If after approximately the midway point of the first 30 days on ZX008 0.2 mg/kg/day there is a clinically meaningful worsening in seizure type, frequency, and/or duration compared with the recent treatment in the core study, the investigator, in consultation with the Medical Monitor, may increase the dose to 0.4 mg/kg/day (maximum 30 mg/day for subjects who are not receiving concomitant STP; 20 mg/day for subjects who are receiving concomitant STP). A clinically meaningful worsening would be an increase in frequency, severity or duration of existing seizures, or emergence of a new seizure type. The description of the clinical worsening must be documented in the source notes and case report form (CRF). Further increase to 0.8 mg/kg/day (maximum 30 mg/day for subjects who are not receiving concomitant STP and to 0.5 mg/kg/day (maximum 20 mg/day) for subjects who are receiving concomitant STP) could also be undertaken for the same conditions after a minimum of 4 days on 0.4 mg/kg/day, if the condition has not stabilized on the 0.4 mg/kg/day dose. Dosing outside of the specified range (ie, 0.2 to 0.8 mg/kg/day or 0.5 mg/kg/day for subjects who are receiving concomitant STP) may be considered after consultation between the investigator and Medical Monitor.

A follow-up ECG and ECHO will be performed 3 and 6 months after study drug discontinuation for early termination and for those subjects who complete the study.

Caregivers will use a diary daily to record the number/type of seizures, dosing, and use of rescue medication. A schedule of assessments is provided in [Table 1](#) and [Table 2](#).

After at least 1 year of treatment in Study 1503 subjects who participated in one of the core studies will transition to a separate extension study (Study 1900) once that study is approved and the study site is initiated. Continuation in a separate extension protocol will be based on benefit/risk and continued eligibility criteria being met. De novo subjects must have participated in this trial for at least 3 months with at least 1 ECHO completed and continue to meet eligibility requirements to be eligible to transition to a separate extension protocol. Alternatively, subjects will transition to commercial product once it is available. For subjects who are entering the separate extension trial or who transition to commercially available drug, post-dosing and cardiac safety follow-up visits are not required in this trial. Subjects who transition to commercially available drug must have an ECHO within 3-6 months before starting commercial drug and will have follow-up ECHOs within the required timeframe while on commercial drug.

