### 5.6 PRIOR AND CONCOMITANT MEDICATION

All prior and concomitant medication will be collected in the CRF.

All medications taken by a subject after the first administration of IMP are regarded as concomitant medication and must be documented in the CRF, including over-the-counter medication, herbal and vitamin/supplement preparations.

Subjects are required to take at least one concomitant AED throughout the study. During at least the first 6 months of the study, subjects will continue to receive their existing AEDs at the same dose as prior to initiating this study. However, once the subject has been stable on a ZX008 dose for at least 6 months with good seizure control, investigators will be allowed as per typical clinical practice to alter one or more other concomitant AED doses as deemed clinically appropriate. Concomitant AEDs may be withdrawn completely but all subjects must remain on a minimum of 1 concomitant AED plus ZX008. No new concomitant AEDs may be introduced while in this study. All medication dose changes must be documented with a clinical explanation and justification. Concomitant AED dose adjustments outside of these parameters should be discussed with the Medical Monitor prior to initiation.

Non-study medications and therapies that are considered necessary for the subject's welfare and will not interfere with the response to the study medication may be given at the discretion of the investigator, informing the Medical Monitor as soon as possible.

It should be noted for any subject receiving hypoglycemic agents, the investigator should consider diabetic medication changes in the setting of weight loss and hypoglycemia.

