### 5.6.1 Vagal Nerve Stimulation

Subjects receiving treatment with vagal nerve stimulation (VNS) may be included as long as the VNS has been in place for at least 6 months prior to entry into the core study, or for de novo subjects prior to first dose in the OLE, and stimulation parameters have been kept constant for 4 weeks prior to core study Visit 1. During at least the first 6 months of the study, VNS stimulation parameters will be kept constant. However, once the subject has been stable on a ZX008 dose for at least 6 months with good seizure control, investigators will be allowed as per typical clinical practice to alter VNS stimulation parameters as deemed clinically appropriate. All VNS stimulation parameter changes must be documented with a clinical explanation and justification. VNS stimulation parameter adjustments outside of these boundaries should be discussed with the Medical Monitor prior to initiation. The subject's use of VNS will be recorded in the CRF.

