### 5.6.2 Ketogenic Diet

Adherence to the KD, or a modified version of KD, is permitted during the study if the dietary habits were initiated more than 4 weeks prior to entry into the core study, or for de novo subjects 4 weeks prior to first dose in the OLE. During at least the first 6 months of the study, the KD will be adhered to. However, once the subject has been stable on a ZX008 dose for at least 6 months with good seizure control, investigators will be allowed as per typical clinical practice to alter the KD as deemed clinically appropriate. All KD changes must be documented with a clinical explanation and justification. KD adjustments outside of these parameters should be discussed with the Medical Monitor prior to initiation. The subject's use of KD will be recorded in the CRF.

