### 10.5.2 Effectiveness Analyses

#### 10.5.2.1 Key Effectiveness Analysis

The key effectiveness endpoint is the change in the convulsive seizure frequency per 28 days between the pre-ZX008 Baseline and OLE Treatment Period. The frequency of convulsive seizures during a given period will be derived from the number and type of events recorded in subject diaries. The seizure frequency per 28 days will be calculated as the number of seizures recorded divided by the number of days in the period and multiplied by 28. The convulsive

seizure frequency will be calculated from all available data collected during either the pre-ZX008 Baseline or OLE Treatment Periods.

Both the mean and median frequency of convulsive seizures will be presented for the pre-ZX008 Baseline Period and the OLE Treatment Period. The significance of the change between periods will be assessed using an analysis of covariance (ANCOVA) model with age group (< 6 years, ≥ 6 years) as a factor and with pre-ZX008 baseline frequency as a covariate. Other factors may be included in the model if they are found to be informative during analyses of the core studies.

Since the ANCOVA relies on assumptions of normality, the key effectiveness endpoint will also be analyzed using a nonparametric method that does not require as stringent assumptions. A test such as the stratified Wilcoxon signed rank test will be used to assess the change from baseline while stratifying by age group.

An additional analysis will be performed to assess the sensitivity of the key effectiveness analysis to changes in dose or type of concomitant AED medications that may occur during the course of the trial. Specifically, the analysis will be repeated with a factor added to the model to indicate whether a subject had a change in prescribed dose or type of concomitant AED medication during the OLE Treatment Period. Further exploratory analyses may be conducted if changes in concomitant AED medication appear to have a significant impact on the effectiveness of ZX008.

Only subjects from Studies ZX008-1501, ZX008-1502, and Cohort 2 of ZX008-1504 will be included in change from baseline analyses of effectiveness. Subjects from Study ZX008-1504 Cohort 1 will be excluded from such analyses since they will enter the OLE Treatment Period without first participating in a baseline period that includes a formal assessment of pre-ZX008 seizure frequency.

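### Sections disagree on whether good seizure control is required before concomitant AED changes; separately, the AED sensitivity analysis uses one factor that cannot tell increases from reductions (minor)

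*Protocol*

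**What the plan says.** **When AEDs may be changed.** The synopsis and Section 3.1 use the same rule: "if a subject has been stable on the same dose of ZX008 for 6 months or longer, investigators may adjust the doses" of other AEDs. Neither mentions seizure control. Section 5.6 gives the investigator that freedom only "once the subject has been stable on a ZX008 dose for at least 6 months with good seizure control". The two sections on other epilepsy treatments carry the same extra condition: "at least 6 months with good seizure control, investigators will be allowed as per typical clinical practice to alter VNS stimulation parameters" (Section 5.6.1) and "at least 6 months with good seizure control, investigators will be allowed as per typical clinical practice to alter the KD" (Section 5.6.2).

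**What happens outside the rule.** Section 5.6 does not forbid other changes. It says: "Concomitant AED dose adjustments outside of these parameters should be discussed with the Medical Monitor prior to initiation". Section 3.1 has the same sentence. The synopsis weakens it by asking for the discussion only if possible. All three places require a reason to be recorded, in Section 5.6 as "All medication dose changes must be documented with a clinical explanation and justification". All three also bar new AEDs and allow complete withdrawal as long as one AED remains.

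**How AED changes enter the analysis.** Section 10.5.2.1 repeats the key effectiveness model after one addition: "a factor added to the model to indicate whether a subject had a change in prescribed dose or type of concomitant AED medication". The indicator covers changes made in the OLE Treatment Period. The section then adds: "Further exploratory analyses may be conducted if changes in concomitant AED medication appear to have a significant impact on the effectiveness of ZX008".

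**The concern.** The first point is one of conduct. The sections part company for the subject most likely to be considered for an AED increase, namely one who has been on the same ZX008 dose for six months and is still having too many seizures. A site working from Section 3.1 would act alone, while a site working from Section 5.6 would call the Medical Monitor first.

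The second point is one of analysis, and does not depend on the first. There is a single treatment group and no comparator (Sections 5.2 and 10.3), and effectiveness is judged as change from a pre-ZX008 baseline. If an AED increase prevents seizures, those seizures count as a ZX008 benefit. The sensitivity analysis exists to show whether AED changes matter. A factor that records only whether a change happened, and not which way it went, may fail to show it. Section 1.10 already uses interim data from this study to say that the effect is maintained without tolerance, so the question has practical weight.

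**Working it through.** The protocol gives no figure on this point, so there is nothing to reproduce. The check is a comparison of the texts, followed by the algebra of the factor.

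**Step 1: the texts side by side.** Take a subject who has had an unchanged ZX008 dose for six months and has poor seizure control.

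| Place | Six months on one dose | Good control required | Route for this subject |
|---|---|---|---|
| Synopsis | yes | no | investigator's discretion |
| Section 3.1 | yes | no | investigator's discretion |
| Section 5.6 | yes | yes | Medical Monitor discussion first |

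In the synopsis and Section 3.1 the word for stability attaches to the ZX008 dose, so it cannot readily be read as clinical stability. Sections 5.6.1 and 5.6.2 side with 5.6, which suggests that the condition is intended and that the two overview texts left it out.

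**Step 2: what the single factor collects.** Sections 3.1 and 5.6 let AED doses be changed in either direction and allow withdrawal. New AEDs are barred, so a change of type within the protocol can only be a withdrawal. One code therefore covers dose increases, dose decreases and withdrawals.

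**Step 3: what the factor estimates.** Let p be the share of subjects with a change whose change was an increase. Let d_inc and d_dec be the mean outcome differences from subjects without a change, for increases and for decreases or withdrawals. Treating each such subject as having one direction of change, the coefficient is approximately

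b = p × d_inc + (1 − p) × d_dec.

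Assume, for illustration only, equal and opposite differences: d_inc = −d and d_dec = +d. Then b = (1 − 2p) × d:

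- p = 0.3: b = (1 − 0.6) × d = 0.4d
- p = 0.5: b = (1 − 1.0) × d = 0
- p = 0.7: b = (1 − 1.4) × d = −0.4d

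If the signs are reversed, because increases go to subjects who are doing badly and reductions to those doing well, then b = (2p − 1) × d and the cancellation is the same size. If both differences have the same sign there is no cancellation. The protocol gives no value for p, d_inc or d_dec, so this shows a mechanism and not an amount.

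**Step 4: how much of the follow-up is exposed.** Section 5.6 holds AED doses for at least the first six months. Over the 36-month OLE Treatment Period used by the key analysis, discretionary changes can affect at most 36 − 6 = 30 months (30/36 = 83%). Over Year 1, used in the secondary objectives, they can affect at most about 12 − 6 = 6 months (50%). Both are upper limits, because the six months on one dose must follow the last ZX008 dose change, and subjects may leave for the separate extension or commercial product before Month 36.

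**The case against.** **On the wording.** A site that follows Section 5.6 also complies with the synopsis and Section 3.1, so the texts can be obeyed together, and 5.6 is the dedicated medication section. The only practical difference is whether a discussion comes first. The affected group is also narrow: Section 3.1 lets the investigator raise ZX008 when seizures warrant it, and Section 4.4 provides for discontinuation on clinically significant worsening. Poor control on an unchanged dose for six months therefore mainly describes subjects at the dose limit or limited by tolerability. All of this stands and keeps the point small. It does not remove the difference between sections.

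**On the factor.** Section 10.5 leaves the full description of methods to an SAP that is not shown, and Section 10.5.2.1 foresees further analyses without tying them to the factor's coefficient. The latter stands: some other signal could prompt them. But the protocol does not leave the coding open. It names one factor for whether any change occurred, while the further analyses are optional and unspecified.

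**Stronger readings that the protocol does not support.** A reader might infer that Section 5.6 prohibits AED increases in poorly controlled subjects; it only sends them to a discussion. A reader might also infer that AED increases have inflated the ZX008 effect, or want a figure for the chance that the factor misses it. Nothing in the protocol gives the number, direction or effect of AED changes. A power figure would rest on invented effects and would ignore that subjects given an increase probably differ in seizure control from those who were not.

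**Conclusion.** Both parts hold, and both are minor.

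The difference between the synopsis and Section 3.1 on one side and Section 5.6 on the other is a matter of plain text. Its consequence is that the same subject can be handled with or without prior Medical Monitor discussion.

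The single any-change factor can understate AED influence when increases and reductions act in opposite directions. How far it does so is unknown. The conclusion assumes only that changes in both directions occur, which the protocol permits, and that their differences from unchanged subjects have opposite signs.

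The impact is limited because the primary objective is safety, effectiveness is secondary, no new AEDs may be introduced, and each change must be justified. Aligning the wording would not keep AED increases out of the baseline comparison, since Section 5.6 still allows them. Nor would it remove all variation between sites, because Sections 5.6 to 5.6.2 do not define good seizure control.

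**What to change.** 1. In the synopsis and Section 3.1, add the good-seizure-control condition to the sentence on AED changes, so that they match Sections 5.6, 5.6.1 and 5.6.2.
2. In the synopsis, delete *if possible* from the sentence on Medical Monitor discussion, so that it matches Sections 3.1 and 5.6.
3. In Section 10.5.2.1, replace the any-change factor with one by direction (none; increase; decrease or withdrawal), derived from the recorded concomitant medication data.
4. As a supplementary analysis only, repeat the key analysis using diary data up to the first AED increase. This is useful alongside the split factor, which remains affected by the reasons for which increases are given. The report should state that it shortens follow-up and drops late data in subjects who may be losing response, so it cannot replace the main analysis.

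The cost is three small wording edits, one changed sensitivity analysis and one added. AED changes and daily seizures are already recorded, so no new data or visits are needed.
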